#### 7.1.1.3 Adverse events list of Dexamethasone

Events that have occurred in 10-15% of individuals treated with dexamethasone include increased appetite, weight gain, sleep disturbance, hypertension, fluid retention, ankle swelling, bruising, infection, mood changes, slow wound healing, depression, and hyperglycemia, which may lead to fatigue, weight loss, excessive thirst and frequent urination. Events that have occurred in 1-9% of individuals treated with dexamethasone include loss of appetite, muscle twitching, increased thirst, frequent urination, increased perspiration, diarrhea, nausea, headache, bone thinning, spinal fracture or fracture of bones, tachycardia, fungal infections. Events that have occurred in <1% of individuals treated with dexamethasone include blurred vision, personality changes, stomach ulcers with bleeding that may cause hematemesis, blood in the stool and abdominal pain. Other, less frequent, events may include bowel perforation, irritation and bleeding of the esophagus, heart failure, allergic reaction that may lead to facial redness, shortness of breath, abdominal cramps and hypotension, convulsions, brain swelling, dizziness, cataracts, glaucoma and increased blood pressure in the eye, development of diabetes, pancreatic inflammation, abdominal swelling, hypokalemia, DVT or PE, malaise, swelling and/or redness of skin, allergic skin reactions, itching, hirsutism, muscle weakness or loss of muscle mass, rupture of tendons, menstrual cycle disturbances, facial puffiness, leading to the appearance of a

CONFIDENTIAL

This document is confidential. Do not disclose or use except as authorized.

“moon face” hormonal disturbances, and hiccups.

## 7.2 Adverse Event Characteristics

- **CTCAE term (AE description) and grade:** The descriptions and grading scales found in the revised NCI Common Terminology Criteria for Adverse Events (CTCAE) version 4.0 will be utilized for AE reporting. All appropriate treatment areas should have access to a copy of the CTCAE version 4.0. A copy of the CTCAE version 4.0 can be downloaded from the CTEP web site [http://ctep.cancer.gov/protocolDevelopment/electronic\\_applications/ctc.htm](http://ctep.cancer.gov/protocolDevelopment/electronic_applications/ctc.htm).
- **For expedited reporting purposes only:**
  - AEs for the agent(s) that are listed above should be reported only if the adverse event varies in nature, intensity or frequency from the expected toxicity information which is provided.
  - Other AEs for the protocol that do not require expedited reporting are outlined in the next section (Expedited Adverse Event Reporting) under the sub-heading of Protocol-Specific Expedited Adverse Event Reporting Exclusions.
- **Attribution of the AE:**
  - Definite – The AE is *clearly related* to the study treatment.
  - Probable – The AE is *likely related* to the study treatment.
  - Possible – The AE *may be related* to the study treatment.
  - Unlikely – The AE is *doubtfully related* to the study treatment.
  - Unrelated – The AE is *clearly NOT related* to the study treatment.

## 7.3 Expedited Adverse Event Reporting

Investigators **must** report to the Overall PI any serious adverse event (SAE) that occurs after the initial dose of study treatment, during treatment, or within 30 days of the last dose of treatment on the local institutional SAE form.

For multi-institution studies where a DF/HCC investigator is serving as the Overall Principal Investigator, each participating institution **must** abide by the reporting requirements set by the DF/HCC. This applies to any medical event equivalent to an unexpected grade 2 or 3 with a possible, probable or definite attribution, all grade 4 toxicities, and grade 5 (death) regardless of study phase or attribution.

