## SYNOPSIS

Study Rationale	Early therapeutic interventions in patients with smoldering MM will prevent/delay progression to overt MM. Recent studies of a phase III trial of lenalidomide and dexamethasone vs. placebo showed improved response, progression free survival and overall survival in patients with high risk SMM compared to placebo control. Therefore, there is a need to examine novel therapeutic combinations in patients with high risk smoldering MM. Based on the activity of lenalidomide and dexamethasone in patients with high risk SMM and based on the safety and activity profile of elotuzumab and lenalidomide in patients with relapsed MM, we propose to examine the activity of elotuzumab and lenalidomide in patients with high risk SMM. We will identify the role of early intervention on prevention of progression in patients with high-risk SMM who have a 50% rate of progression at 2 years.
Products	Elotuzumab is a humanized recombinant monoclonal IgG1 antibody product directed to human SLAMF7 (CD2-subset-1, also known as CRACC), a cell surface glycoprotein that is highly expressed in MM cells. Lenalidomide (REVLYMID®), a thalidomide analogue, is an immunomodulatory agent with antiangiogenic properties. Dexamethasone is a synthetic adrenocortical steroid.
Study Objectives	Primary Objectives 

To determine the proportion of high risk smoldering multiple myeloma patients who are progression free at 2 years after receiving elotuzumab, lenalidomide and dexamethasone combination therapy

 Secondary Objectives 

To assess the response rate of the combination in these patients

To assess time to progression

To assess duration of response

To assess overall survival

To assess safety of the combination

To examine molecular evolution of the tumor cells

To determine the role of immune cells in the progression of smoldering MM

To determine minimal residual disease (MRD)

Efficacy Endpoints	Response will be assessed using the IMWG criteria for response in Multiple Myeloma.
Safety Endpoints	AEs will be evaluated during the treatment period using CTCAE v4.03.
Study Design	This is a phase II study using the combination of elotuzumab, lenalidomide and dexamethasone in patients with high-risk smoldering multiple myeloma.

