## 5.6 Duration of Follow Up

Participants will be followed for up to **3 years** after removal from protocol therapy or until progression to active symptomatic MM, whichever occurs first. Assessments will be performed every 3 to 6 months ( +/- 28 days ) for up to 3 years. Patients who have undergone stem cell mobilization will also be followed for 3 years after removal from protocol therapy or until progression to active symptomatic myeloma, whichever occurs first. Participants removed from protocol therapy for unacceptable adverse event(s) will be followed until resolution or stabilization of the adverse event.

Participants unable to participate in follow up every 3 months may follow up every 6 months at PI discretion in accordance with standard of care follow-up frequency and COVID precautions. Physical exams and correlative blood draws that are not done due to virtual visits will not be considered violations. Local myeloma labs must be provided to the participating site for data entry purposes. Bone marrow biopsy and scans are strongly recommended yearly after EOT, but not require however, scans and bone marrow biopsy and research samples are required at time of suspected disease progression

The following is required during the Active Follow Up period (for up to 3 years):

1. Physical exams are voluntary during this period
  - a. Virtual visits/telehealth visits are acceptable
2. SPEP and Immunofixation
3. Serum Free Light Chains (SFLC)
4. UPEP and Immunofixation only for those where disease is tracked by the urine
5. Serum Immunoglobulin test
6. PET/CT assessments are strongly recommended yearly and is required at the time of suspected progression
  - a. The same assessment modality should be used consistently across the duration of the trial
7. Bone marrow biopsies are and strongly recommended yearly after EOT and is required at the time of suspected progression
8. Research bone marrow samples will be collected at the time of any bone marrow biopsy/aspirate procedure
9. Research blood will be collected whenever an in person visit to the site occurs. Research blood samples that are not collected at time points in the collection calendar due to COVID precautions or q6 month follow up will not be considered violations unless it is missed at the time of suspected progression.
10. Response
11. CRAB/MDE Assessment
12. Bone marrow biopsy/aspirate results and cytogenetics/FISH if ordered
13. Scan results and modality

CONFIDENTIAL

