This document is confidential. Do not disclose or use except as authorized.

Participants who come off active follow up when they pursue other SMM or MM directed therapy will be followed for survival indefinitely which will capture survival stats, and subsequent therapy information.

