#### 7.1.1.2 Adverse Event List for Lenalidomide

Events that have occurred in >10% of individuals treated with lenalidomide include neutropenia, anemia, thrombocytopenia, fatigue, rash, diarrhea, constipation, nausea, loss of appetite, itching, dry skin, muscle cramps, lack or loss of strength, dizziness, insomnia, swelling of the extremities, headache, back and joint pain, fever, cough, upper respiratory infection, and dyspnea.

Events that have occurred in >1% of individuals treated with lenalidomide include risk of DVT, PE, and blood clots that could lead to stroke, heart attack, or organ failure, febrile neutropenia, atrial fibrillation, pneumonia or lung infections, sepsis, dehydration and renal failure.

Events that have occurred in <1% of individuals treated with lenalidomide include rare treatment-emergent adverse events of angioedema, serious skin reactions including Stevens-Johnson syndrome (SJS) and toxic epidermal necrolysis (TEN) or an allergic skin reaction similar to that seen with thalidomide, tumor lysis syndrome (TLS), tumor flare reaction (TFR), and rhabdomyolysis. In addition, lenalidomide has been shown to increase the level of digoxin in the blood in some patients. Patients will be instructed to inform their doctor if taking digoxin.

There may be an increased risk of second cancers in patients who are on lenalidomide maintenance therapy after a bone marrow transplant.

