## 7.9 Routine Adverse Event Reporting

All Adverse Events **must** be reported in routine study data submissions to the Overall PI on the toxicity case report forms. **AEs reported through expedited processes (e.g., reported to the IRB, FDA, etc.) must also be reported in routine study data submissions.**

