## 10. STUDY CALENDAR

Screening evaluations are to be conducted within 28 days prior to initiation of registration. Protocol therapy should start as soon after registration as feasible. Baseline assessments are to be conducted on C1D1 of initial therapy and should be considered separate from screening evaluations. Evaluations need not be repeated for C1D1 if screening evaluations are performed within 7 days of registration. Scans and bone marrow assessments do not need to be repeated if performed within 6 weeks of registration. All assessments must be performed prior to administration of any study medication.. See below for detailed scheduled of assessments. Study medications will be administered according to the schedule and guidelines outlined in Section 5.

	Pre-registration		Cycles 1-24 (28 days) 				Follow Up 
Tests and procedures	≤ 28 days prior to registration	≤ 21 days prior to registration	Day 1 of all cycles	Days 8, 15 and 22 of cycles 1 & 2	Cycle 9 Day 1/ Or to confirm CR^9	End of Tx	Every 3 or 6 Months (+/- 28 days)
				Days 1 &15 from cycle 3-8			
History and exam, height, weight. Performance Status	X		X			X	(X)
Toxicity Notation			X			X	
Hematology group (WBC w/ diff, PLT, Hgb, ANC)		X	X	X		X	X
Chemistry 		X	X	X		X	X
Direct & total bilirubin 		X	X			X	
Free light chain assay		X	X			X	X
Serum and Urine Immunofixation (SPEP and UPEP) with quantitative immunoglobulins 		X	X			X	X
β2M, CRP, LDH		X				X	
Metastatic Bone Survey/ Spine MRI or PET/CT 	X					X	(X)
EKG		X				X	
Serum pregnancy test		X					
Unilateral bone marrow aspirate and biopsy 	X				X	X	(X)
Research bone marrow aspirate 	X 				X 	X 	(X)
Research Blood 	X 		X		X	X	(X)

1- Cycle 1, Day 1 laboratory values need to meet eligibility criteria

2- Direct bilirubin to be obtained if total bilirubin is abnormal.

3- Scheduling allows for +/- 3 days cycles 1-2 and +/- 7 days for cycle 3 and beyond.

4- Chemistry includes sodium, potassium, chloride, bicarbonate, bun, creatinine, calcium, glucose, albumin, ALT (SGPT), total protein, AST (SGOT), total bilirubin, magnesium, and phosphorus.

5- These procedures should also be done at any time during the course of the study to confirm CR.

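### A second cancer arising after treatment has no required, systematic ascertainment, and the sections disagree on when adverse event collection ends

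*Combined protocol and SAP*

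**What the plan says.** Safety of the combination is a secondary objective (section 1.3). The collection windows are set in several places.

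- **Synopsis, Safety Endpoints:** "AEs will be evaluated during the treatment period using CTCAE v4.03".
- **Section 7.3:** sites must report to the Overall PI any serious adverse event "that occurs after the initial dose of study treatment, during treatment, or within 30 days of the last dose of treatment".
- **Section 7.9:** all adverse events must "be reported in routine study data submissions to the Overall PI on the toxicity case report forms". No end date is given.
- **Sections 7.6 and 7.7:** serious adverse events go to the two drug suppliers, also with no stated cut-off after the last dose.
- **Section 10, study calendar:** the row "Toxicity Notation" is marked on Day 1 of all cycles and at End of Tx. The Follow Up column is blank for that row, although hematology, chemistry and free light chains are marked there.
- **Section 5.6, active follow-up:** 13 items are listed as required, covering visits, disease laboratory tests, imaging, marrow, research samples, response and CRAB/MDE status. None concerns toxicity or second cancers. Physical exams are voluntary and telehealth visits are accepted. There is one exception for events already known: "Participants removed from protocol therapy for unacceptable adverse event(s) will be followed until resolution or stabilization of the adverse event".
- **Section 5.6, survival follow-up:** participants who go on to other therapy are followed indefinitely, "which will capture survival stats, and subsequent therapy information".
- **Section 13.1.2:** the Safety Population is any patient with one dose. No observation window is stated.

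The lenalidomide list in section 7.1.1.2 says: "There may be an increased risk of second cancers in patients who are on lenalidomide maintenance therapy after a bone marrow transplant".

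**The concern.** The trial gives up to 16 maintenance cycles of lenalidomide to people without symptomatic disease, then keeps contact with them for up to 3 years and, for some, longer. Second cancers appear in the protocol's own list of lenalidomide risks. Yet nothing in the required follow-up asks about them. Whether a case found in that period reaches the database would depend on a site volunteering it.

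In this population a late serious harm weighs directly against a delay in progression, so the gap limits what the trial can say about its safety objective. The contacts already exist; what is missing is one data item. Separately, the sections do not agree on where adverse event collection stops, so two sites could reasonably apply different cut-offs.

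**Working it through.** **Inputs from the documents.** 28-day cycles and 24 cycles (sections 5.1 and 5.5); follow-up of up to 3 years, ending at symptomatic progression if earlier (5.6); 30-day window for serious adverse events (7.3); 55 patients, and planning rates of 50% and 70% progression-free at 2 years (13.1 and 13.2).

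**Inputs assumed.** A constant progression hazard; treatment until progression or cycle 24; 0.5 to 3 second cancers per 100 person-years. The documents give no second-cancer rate.

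**Step 1. The plan's own figure.** Read per participant, 24 months of treatment + 36 months of follow-up = 60 months, which matches the synopsis Study Duration. In exact days: 24 × 28 = 672; 3 × 365.25 = 1,095.75; total 1,767.75 days, or 4.84 years (58.1 months).

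**Step 2. Participant on the full schedule.** Uncovered share = (follow-up − 30 days) / (treatment + follow-up).

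- 28-day cycles: (1,095.75 − 30) / 1,767.75 = 60.3%.
- Treatment taken as exactly 2 years: (1,095.75 − 30) / (730.5 + 1,095.75) = 58.4%.
- 28-day cycles without the 30-day allowance (toxicity notation ends at End of Tx): 1,095.75 / 1,767.75 = 62.0%.

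Uncovered time is 1,065.75 / 365.25 = 2.92 years per participant. For 55 patients that is at most 55 × 2.92 ≈ 160 person-years.

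**Step 3. Other courses** (28-day cycles, 30-day allowance, active follow-up only).

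| Course | Uncovered share |
|---|---|
| 2 cycles, then full follow-up | 92.5% |
| 8 cycles, then full follow-up | 80.8% |
| 24 cycles, progression 1 year after treatment | 32.3% |
| Progression on treatment | 0% |

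**Step 4. Cohort average.** Let S be the 2-year progression-free rate, h = −ln(S)/2, c = 702/365.25 = 1.92 years and E = 4.84 years. Expected uncovered time per patient is (e^(−hc) − e^(−hE))/h; expected total active time is (1 − e^(−hE))/h.

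| S | h per year | Uncovered years | Total years | Share | Person-years, 55 patients |
|---|---|---|---|---|---|
| 50% | 0.347 | 0.943 | 2.346 | 40% | 52 |
| 70% | 0.178 | 1.615 | 3.242 | 50% | 89 |
| 90% | 0.053 | 2.44 | 4.28 | 57% | 134 |

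**Step 5. Events without required ascertainment**, at 0.005 to 0.03 per person-year.

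- S = 50%: 52 × 0.005 = 0.3 to 52 × 0.03 = 1.6.
- S = 70%: 89 × 0.005 = 0.4 to 89 × 0.03 = 2.7.
- Maximum: 160 × 0.005 = 0.8 to 160 × 0.03 = 4.8.

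Patients who progress move to survival contact, which has no second-cancer item either. That time is not counted here.

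**The case against.** Several parts of the case on the other side are correct.

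- **The 30-day sentence is narrow.** A reader might infer from section 7.3 that all adverse event recording stops 30 days after treatment. It does not say so. It sets the window for serious adverse event reports to the Overall PI. Section 7.9 covers all adverse events without an end date, sections 7.6 and 7.7 state no cut-off, section 3.9 of Appendix E speaks of events during the course of a study, and events that caused removal are followed further. A late second cancer is therefore not outside every reporting duty.
- **The named risk is qualified.** Section 7.1.1.2 ties it to maintenance after a bone marrow transplant and does not call it delayed. Transplant is not part of this regimen, although section 5.4.1 allows stem cell mobilization for transplant-eligible patients.
- **60% is not a trial-wide share.** It belongs to one course of participation, since active follow-up ends at symptomatic progression.
- **No second-cancer rate is planned.** One might infer that the trial would publish a rate that is too low, but neither the objectives nor section 13.1.2 promises such a rate.
- **Precision would be poor.** In 55 patients, one event gives an exact 95% interval of about 0.05% to 9.7%, and three give 1.1% to 15.1%. The primary decision rule is unaffected. The case report forms are not in the documents, so what they ask is unknown.

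These points narrow the claim but do not close the gap. A duty to report a known event does not make anyone ask about it at follow-up. Sections without an end date, beside a calendar that stops at End of Tx, are inconsistent rather than reassuring. Capture that is permitted but not required would vary by site.

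**Conclusion.** The point holds as a gap in ascertainment and an inconsistency in the stated end of collection. Followed as written, the plan would not systematically detect a second cancer arising more than 30 days after the last dose.

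The uncovered share is about 60% of planned observation for a participant who completes 24 cycles and 3 progression-free years (58.4% to 62.0%, depending on how cycles and the 30 days are counted). Over the cohort it is about 40% to 50% of active person-time at the two planning rates, or 52 to 89 person-years, with 160 as the ceiling. These averages rest on a constant hazard and on treatment continuing to progression or cycle 24; stopping treatment early without progression would raise the share. The event counts, about 0.3 to 2.7 and at most 4.8, rest also on an assumed incidence that the documents do not supply.

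The documents do not support saying that adverse event recording as a whole ends at 30 days, that 60% of the trial's observation is lost, or that a planned second-cancer rate would be biased. This is an inexpensive improvement to a secondary objective, with no effect on sample size or the primary analysis.

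**What to change.** 1. Add one required item, second primary malignancy (type and date, regardless of attribution), to the active follow-up list in section 5.6, the Follow Up column of the calendar in section 10, and the survival contact in section 5.6.
2. State one end of adverse event and serious adverse event collection, and use it consistently in the synopsis and sections 5.6, 7.3, 7.6, 7.7, 7.9 and 10.
3. In section 13.1.2, report the number and timing of second cancers from first dose in the Safety Population. If there are enough events, add the cumulative incidence with death as a competing event.

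The cost is one case report form item at contacts that already take place, one table, and editing to align the sections. No visit or procedure is added. The resulting estimate will be imprecise because few events are expected, and the report should say so.

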## 7.4 DF/HCC Expedited Reporting Guidelines

Investigative sites within DF/HCC and DF/PCC will report SAEs directly to the DFCI Office for Human Research Studies (OHRS) per the DFCI IRB reporting policy.

Other investigative sites will report SAEs to their respective IRB according to the local IRB's policies and procedures in reporting adverse events. A copy of the submitted institutional SAE

CONFIDENTIAL

This document is confidential. Do not disclose or use except as authorized.

form should be forwarded to the Overall PI within the timeframes detailed in the table below.

DF/HCC Reportable AEs					
Attribution	Gr. 2 & 3 AE Expected	Gr. 2 & 3 AE Unexpected	Gr. 4 AE Expected	Gr. 4 AE Unexpected	Gr. 5 AE Expected or Unexpected
Unrelated Unlikely	Not required	Not required	5 calendar days #	5 calendar days	24 hours*
Possible Probable Definite	Not required	5 calendar days	5 calendar days #	5 calendar days	24 hours*
# If listed in protocol as expected and not requiring expedited reporting, event does not need to be reported.					
* For participants enrolled and actively participating in the study or for AEs occurring within 30 days of the last intervention, the AE should be reported within 1 business day of learning of the event.					

The Overall PI will submit SAE reports from outside institutions to the DFCI OHRS according to DFCI IRB policies and procedures in reporting adverse events.

If, following initiation of the investigational product, it is subsequently discovered that a study subject is pregnant or may have been pregnant at the time of investigational product exposure, including during at least 6 half lives after product administration, the investigational product will be permanently discontinued in an appropriate manner (e.g., dose tapering if necessary for subject safety).

Protocol-required procedures for study discontinuation and follow-up must be performed on the subject unless contraindicated by pregnancy (e.g., x-ray studies). Other appropriate pregnancy follow-up procedures should be considered if indicated. The investigator must immediately notify the BMS, Celgene (or designee) Medical Monitor of this event and complete and forward an SAE Form to BMS and Celgene (or designee) within 24 hours and in accordance with SAE reporting procedures described in this section.

